3.0 OBJECTIVES & HYPOTHESES

3.1 Primary Objective & Hypothesis

Objective: To evaluate whether one administration of pembrolizumab (Keytruda®) is able to alter biomarkers related to intratumoral immunity (i.e. the amount of TILs, PD-L1 and CD73 expression) and proliferation (i.e. Ki67 expression) in early breast cancer

Hypothesis: One administration of pembrolizumab (Keytruda®) will result in an increase in the amount of TILs and a decrease in the expression of PD-L1, CD73 and Ki67 in a subgroup of patients with early breast cancer.

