(4) **Objective:** To evaluate whether one administration of pembrolizumab (Keytruda®) causes a significant shift in T-cell subsets in peripheral blood.

Hypothesis: One administration of pembrolizumab (Keytruda®) causes a significant shift in T-cell subsets in peripheral blood.

(5) **Objective:** To evaluate whether baseline PD-L1 expression and amount of TILs are predictive for the effect of pembrolizumab (Keytruda®) and/or response to neo-adjuvant chemotherapy.

Hypothesis: Tumors with a high baseline PD-L1 expression and a high amount of TILs are more likely to respond to pembrolizumab (Keytruda®) and/or response to neo-adjuvant chemotherapy than tumors with a low baseline PD-L1 expression and/or a low amount of TILs.

RETROSPECTIVE STUDY:

(6) **Objective:** To evaluate whether baseline expression of PD-L1, CD73, Ki67 and the amount of TILs can predict distant metastasis free survival.

Hypothesis: Low expression of PD-L1, CD73 and Ki67 and a high amount of TILs are associated with a better distant metastasis free survival.

(7) **Objective:** To evaluate whether there is an association between expression of PD-L1, CD73, Ki67 and the amount of TILs.

Hypothesis: There is an association between expression of PD-L1, CD73, Ki67 and the amount of TILs.

(8) **Objective:** To evaluate whether the immunohistochemical analysis of PD-L1, CD73, Ki67 and TIL count on core biopsy specimens reflects accurately the expression of these markers on tumor resection specimen.

Hypothesis: The immunohistochemical analysis of PD-L1, CD73, Ki67 and TIL count on core biopsy specimens reflects accurately the expression of these markers on tumor resection specimen.

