This phase 0 study allows short-term evaluation of the effect of anti-PD1 therapy in early breast cancer with biomarker determination by comparing histological markers pre-treatment and at surgery.

Changes in biomarkers related to intratumoral immunity and proliferation may provide evidence for biological activity of pembrolizumab (Keytruda®) and may allow the development of a blood-based biomarker to help predict which patients may benefit from Pembrolizumab (Keytruda®) and to monitor therapy response.

To evaluate whether neo-adjuvant chemotherapy can alter expression of biomarkers related to intratumoral immunity and proliferation, patients will also be enquired to provide a new core biopsy after the last dose of chemotherapy.

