5.1.2 Subject Inclusion Criteria

In order to be eligible for participation in this trial, the subject must:

1. Be willing and able to provide written informed consent/assent for the trial.
2. Be ≥ 18 years of age on day of signing informed consent.
3. Be willing to provide tissue from a newly obtained core or excisional biopsy of a tumor lesion if needed. *Newly obtained is defined as a specimen obtained up to 6 weeks (42 days) prior to initiation of treatment on Day 0. Subjects for whom newly obtained samples cannot be provided (e.g. inaccessible or subject safety concern) may submit an archived specimen only upon agreement from the Sponsor.*
4. Have a performance status of 0 or 1 on the ECOG Performance Scale.
5. Have non-metastatic operable newly diagnosed primary invasive carcinoma of the breast that is:
 - a. Histologically confirmed
 - b. ER/PR negative or ER positive breast cancer with TIL expression on core biopsy. ER/PR status will be evaluated with Allred score (semi-quantitative measurement) following ASCO CAP guidelines 2009. TIL count based on the guidelines of the International TILS Working Group on Breast Cancer
 - c. HER2 negative or positive. HER2 status will be evaluated using IHC followed by FISH with dual probe (ASCO CAP guidelines 2013).

- d. Primary tumor size greater than 1 cm, measured by any of clinical examination, mammography, ultrasound or magnetic resonance imaging
 - e. Any clinical nodal status
6. Have evaluable core biopsy for IHC
 7. Be willing to provide plasma/blood samples
 8. After neo-adjuvant chemotherapy (cohort B1 and B2) patients must have residual tumor >1cm and must be willing to provide evaluable new tumor biopsy for IHC
 9. Demonstrate adequate organ function as defined in Table 1, all screening labs should be performed within 14 days of treatment initiation.

Table 1 Adequate Organ Function Laboratory Values

System	Laboratory Value
Hematological	
Absolute neutrophil count (ANC)	≥1,500 /mcL
Platelets	≥100,000 / mcL
Hemoglobin	≥9 g/dL or ≥5.6 mmol/L without transfusion or EPO dependency (within 7 days of assessment)
Renal	
Serum creatinine OR Measured or calculated ^a creatinine clearance (GFR can also be used in place of creatinine or CrCl)	≤1.5 X upper limit of normal (ULN) OR ≥60 mL/min for subject with creatinine levels > 1.5 X institutional ULN
Hepatic	
Serum total bilirubin	≤ 1.5 X ULN OR Direct bilirubin ≤ ULN for subjects with total bilirubin levels > 1.5 ULN

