5.2.2 Study cohorts prospective trial

The trial design for each cohort is displayed below.

All patients will receive 1 administration of pembrolizumab 10 +/- 4 days before surgery

Cohort A

Cohort B

Patients must:

- Have ER/PR negative or ER positive breast cancer > 1 cm, **and**
- Have received anthracycline-taxane neo-adjuvant chemotherapy, **and**
- Have residual tumor > 1 cm after neo-adjuvant chemotherapy, **and**
- Provide evaluable new tumor biopsy for IHC, **and**
- Provide a blood sample

Patients will be enrolled

D0: administration of Pembrolizumab 200 mg

D10 ± 4: surgery + provide blood sample

Trial treatment should begin on the day of randomization or as close as possible to the date on which treatment is allocated/assigned.

New tumor biopsy only necessary for cohort B, but will be collected as well in cohort A for further research requiring fresh material, in case patients of cohort A are willing to provide a new fresh tumor sample (with biopsy).

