8.2 Statistical analysis plan

Retrospective study:

Product: MK-3475
Protocol/Amendment No.:

Pearson correlations will be used to analyze the association between expression of PD-L1, CD73, Ki67, the amount of TILs, and other relevant functional immunoparameters. Linear regression analysis will be applied to estimate the predictive value of the core needle biopsy expression measurements of PD-L1, CD73, Ki67 and TIL count for the expression of the same parameters in the whole tumor as measured by the surgical resection specimens.

Prospective study:

Changes in biomarker levels within patients between measurements before and after the administration of pembrolizumab will be analyzed using paired t-test or Wilcoxon signed rank test, as appropriate depending on the distribution of the measurements.

Differences in evolutions of biomarker expression between cohorts will be estimated using linear models and presented as the mean difference of the change with 95% confidence intervals.

Statistical analysis will be performed by an experienced biomedical statistician at the Interuniversity Centre for Biostatistics and Statistical Bioinformatics.

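### The primary paired test cannot separate a core-to-resection sampling shift from a pembrolizumab effect, and section 8.2 does not report or use the untreated S58910 shift that could inform this for A1/A2

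*Combined protocol and SAP*

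**What the plan says.** Section 3.1 asks whether one dose "is able to alter biomarkers related to intratumoral immunity" (TILs, PD-L1, CD73) and proliferation (Ki67), and expects the change "in a subgroup of patients with early breast cancer".

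Section 5.2.2 leaves no untreated patients in the phase 0 study: "All patients will receive 1 administration of pembrolizumab". Section 4.2.1 describes the evaluation as "comparing histological markers pre-treatment and at surgery". On the baseline side, inclusion criterion 6 in section 5.1.2 is "Have evaluable core biopsy for IHC". Criterion 3 covers a new core or excisional sample and defines newly obtained as a "specimen obtained up to 6 weeks (42 days) prior to initiation of treatment on Day 0".

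Section 8.2 then states: "Changes in biomarker levels within patients between measurements before and after the administration of pembrolizumab will be analyzed using paired t-test", with Wilcoxon as the alternative. The only between-group analysis of the prospective data is between phase 0 cohorts, all of them treated.

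For the retrospective study (S58910), objective (8) in section 3.2 has as its hypothesis that the immunohistochemical analysis of PD-L1, CD73 and Ki67 and the "TIL count on core biopsy specimens reflects accurately the expression of these markers on tumor resection specimen". For this, section 8.2 plans a linear regression of the resection value on the core value, to estimate how well the core predicts the resection. It names no mean difference between the two specimens and does not refer to the prospective analysis.

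**The concern.** The paired test compares the mean change with zero. Zero means no drug effect only if core and resection would give the same mean in an untreated tumor, and the protocol lists that agreement as a question to be answered.

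If the two specimen types differ systematically for a marker, two things can go wrong. A shift in the hypothesised direction can look like a pembrolizumab effect. A shift in the other direction can hide a real effect.

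The untreated data that bear on this are already planned. S58910 patients are ER/PR-negative and had upfront surgery, which is the receptor type and treatment path of cohorts A1 and A2. Following section 8.2 as written, the prospective result would be reported without reference to them.

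**Working it through.** **Inputs from the documents.** Section 8.1 derives 54 from feasibility, not power:
- 600 × 20% = 120 ER/PR-negative; 120 × 25% = 30 upfront surgery; 90 × 45% ≈ 40 with residual disease.
- (30 + 40) × 50% = 35, against 34 stated.
- 400 × 10% × 50% = 20 ER-positive.
- Total 55, against 54 stated; the difference is immaterial.

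The A1/A2 share is 30 × 50% = 15. S58910 has 200 patients.

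**Assumptions, because the documents give no figure.** Two-sided 5%; A1 and A2 tested together; normal data; shift s in SDs of the paired difference; 200, 100 or 50 usable S58910 pairs (m), with equal SDs of change in the two studies.

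**1. Effect of a shift on the paired test.** With no drug effect, the rejection probability comes from a noncentral t with n − 1 degrees of freedom and noncentrality s√n.

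| n | s = 0.1 | 0.2 | 0.3 | 0.5 |
|---|---|---|---|---|
| 10 | 5.9% | 8.8% | 13.6% | 29.3% |
| 15 | 6.5% | 11.2% | 19.2% | 43.8% |
| 20 | 7.1% | 13.6% | 24.7% | 56.5% |

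**2. Masking.** At n = 15 a true change of 0.778 SD has 80% power. With an opposite shift the test sees 0.778 − s, and power is 68.5%, 54.9%, 40.7% and 17.1% for s = 0.1, 0.2, 0.3 and 0.5.

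**3. What the planned regression contains.** A least-squares line passes through both means, so mean shift = intercept + (slope − 1) × mean core. The shift can be recovered, but not from one coefficient. With invented values of mean core 20, slope 0.7 and intercept 6, the shift is 6 + (0.7 − 1) × 20 = 0 despite the non-zero intercept. Conversely, adding a constant 0.5 SD shift to simulated data left slope (0.80) and R² (0.65) unchanged.

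**4. Precision from S58910.** The 95% CI half-width of the untreated shift is t(0.975, m − 1)/√m = 0.14, 0.20 and 0.28 SD for m = 200, 100 and 50. The standard error of the A1/A2 change minus the S58910 change, relative to that of the paired change alone, is √(1 + 15/m) = 1.04, 1.07 and 1.14.

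**5. Behavior of the comparison** (Welch, 40,000 simulated trials, n = 15, m = 200/100/50):
- Common shift of 0.3 SD, no drug effect: Welch rejects in about 5%, the paired test in about 19%.
- True effect 0.778 SD, opposite shift of 0.3 SD: Welch alone rejects in about 78/76/72%. Requiring both tests gives about 40–41%, the same as the paired test alone.
- True effect 0.778 SD, no shift: requiring both lowers power from 80% to about 76/74/69%.
- No drug effect, but the two studies' shifts differ by 0.3 SD: Welch itself rejects in about 16–19%.

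**The case against.** **This is an openly uncontrolled window study.** The trial summary lists type of control as not applicable, and section 4.2.1 says only that changes may provide evidence of biological activity. That stands as context. It does not tell the reader how a before-after change will be read, and the primary objective is still worded as what the drug does.

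**The shift is already in the planned regression.** This stands. The missing items are a reported summary and a cross-reference, not a new analysis.

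**The specimen contrast is partly inferred.** This also stands. No prospective section says which surgical sample is scored, and criterion 3 allows an excisional baseline sample. But no section requires a matched core at surgery.

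**S58910 is an imperfect reference.** Its patients date from 2005–2010 with tumors >2 cm, against >1 cm in the trial. Its biopsy-to-surgery interval and number of core-resection pairs are not stated. In the trial the interval is at least 6 days and, for a newly obtained specimen, up to 42 + 14 = 56 days. This is why the comparison should not be a gate. Requiring significance against S58910 would cost power when there is no shift, would rest on equal shifts in two different studies, and would not recover a masked effect.

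**n = 15 is illustrative.** It is a one-year accrual figure, no pooled A1/A2 test is specified, and enrolment stops at 54 whatever the cohort sizes. The table therefore shows n = 10 and 20 as well.

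A reader might infer that the primary result will be biased, or that comparison with S58910 would prove or disprove a drug effect. The documents support neither: they give no evidence of a shift, its direction or its size, and no basis for assuming that the two studies share one.

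**Conclusion.** The point holds as one of non-separability. With every patient dosed and the specimen normally changing from core to surgical tissue, the section 8.2 test cannot distinguish a sampling shift from a pembrolizumab effect, and the plan neither reports nor uses the untreated S58910 shift.

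The consequence is conditional. Under the stated assumptions at n = 15, false significance ranges from 6.5% (0.1 SD) to 44% (0.5 SD) against a nominal 5%. The between-cohort models are unaffected if the shift is common to all cohorts, but they do not answer the primary objective.

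The remedy has limited reach. It informs about 15 of 54 patients and leaves A3 and all of cohort B unresolved. It should not be presented as restoring power lost to an opposite shift; only the supportive estimate would show a masked effect. This is a cheap improvement, not a fatal flaw.

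**What to change.** Keep the paired test and add to section 8.2:

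- (a) For each of TILs, PD-L1, CD73 and Ki67, the S58910 mean resection-minus-core difference (median where Wilcoxon is used) with 95% CI and the number of pairs, reported beside the A1/A2 change.
- (b) As a supportive estimate only, the A1/A2 change minus the S58910 change with 95% CI. Use unequal-variance standard errors, because section 3.1 expects change in only some patients and the SDs of change may therefore differ. Do not use it as a pass/fail test.
- (c) An interpretation statement. A before-after change is attributed to pembrolizumab only with the sampling caveat. For A1/A2 it is read against the S58910 shift. For A3 and cohort B it cannot be separated from sampling effects, and the S58910 shift is not applied to them.

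State also which surgical sample is scored.

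The cost is SAP wording, one summary table and one estimate per marker. Objective (8) already needs the paired readings, so no new patients, biopsies or staining are required. The difference is estimated with a standard error about 4%, 7% or 14% larger than the paired change for 200, 100 or 50 pairs. The S58910 differences in era, tumor size and possibly interval should be listed beside it.

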3.2 Secondary Objectives & Hypotheses

PROSPECTIVE STUDY:

(1) **Objective:** To evaluate whether anthracycline-taxane based neo-adjuvant chemotherapy is able to alter biomarkers related to intratumoral immunity and proliferation in early breast cancer.

Hypothesis: Administration of anthracycline-taxane based neo-adjuvant chemotherapy will result in an increase in the amount of TILs and a decrease in the expression of PD-L1, CD73 and Ki67 in a subgroup of patients with early breast cancer.

(2) **Objective:** To evaluate whether there is a difference in biomarker evolution after pembrolizumab (Keytruda®) administration in cohort A (upfront surgery, not prior treatment) or cohort B (have received full course of neoadjuvant chemotherapy, and have clear evidence of residual tumor after chemotherapy).

Hypothesis: The change in biomarker expression will be higher in cohort B (having received full course of neoadjuvant chemotherapy, and having clear evidence of residual tumor after chemotherapy) than in cohort A (upfront surgery, not prior treatment).

(3) **Objective:** To evaluate whether there is a difference in biomarker evolution after one pembrolizumab (Keytruda®) administration in triple negative breast cancer (Cohort A1,B1) versus ER/PR negative Her2 positive breast cancer (Cohort A2,B2).

Hypothesis: The change in biomarker expression after pembrolizumab (Keytruda®) administration will be higher in triple negative breast cancer than in ER/PR negative Her2 positive breast cancer.

(4) **Objective:** To evaluate whether there is a difference in biomarker evolution after one pembrolizumab (Keytruda®) administration in triple negative breast cancer (Cohort A1,B1) versus ER positive breast cancer (Cohort A3,B3).

Hypothesis: The change in biomarker expression after pembrolizumab (Keytruda®) administration will be higher in triple negative breast cancer than in ER positive breast cancer.

(5) **Objective:** To evaluate whether there is a difference in biomarker evolution after one pembrolizumab (Keytruda®) administration in ER/PR negative Her2 positive breast cancer (Cohort A2,B2) versus ER positive breast cancer (Cohort A3,B3).

Hypothesis: The change in biomarker expression after pembrolizumab (Keytruda®) administration will be higher in ER/PR negative Her2 positive breast cancer than in ER positive breast cancer

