4.2 Rationale

4.2.1 Rationale for the Trial and Selected Subject Population

There is an urgent need for new treatment strategies in patients with ER/PR negative breast cancer. Different clinical studies with anti-PD-1 therapy show clear evidence of clinical benefit in terms of overall survival, demonstrating immune modulating of ICPs as a promising new

targeted therapy in different types of cancer, even in less immune-driven subtypes of cancer. However, most of these studies are performed in metastatic stages of malignant melanoma, non-small cell lung cancer etc. No studies are available on the response to immune therapy in early stages of cancer. In addition, data on ICPs-expression and the effect of ICP- inhibition therapy (e.g. PD-1 inhibition) are rather scarce in breast cancer, as well as criteria to evaluate response in early stage of disease. Investigation of potential biomarkers is urgently needed to identify the subgroup of patients that will benefit from immunotherapy. This will optimize the therapeutic efficacy, prevent toxicity and reduce the costs associated with immunotherapy.

Tumor cells show increased response to immunotherapy after they became more immunogenic by therapy-induced immunogenic cell death (ICD) e.g. chemotherapy, radiotherapy etc. This process might be of special interest/benefit in less immunogenic-driven tumors. BC has traditionally not been considered as a highly immunogenic neoplasm, but there is increasing evidence for dynamic cross-talk between the host-immune system and BC cells. In addition, certain subgroups of BC (mainly ER/PR negative tumors) display presence of a massive lymphocytic tumor-infiltrate (TILs), which have been shown to be a potential key factor in the response to immunomodulatory therapy. Therefore, anthracycline based chemotherapy, followed by immunotherapy (e.g. PD-1 inhibition therapy) might be promising in BC.

There are currently little data regarding efficacy of immunotherapy in ER+ breast cancers. This subtype is generally considered to be less immunogenic than ER/PR negative breast cancer. The relationship in ER+ breast cancer is more complicated due to the association of TILs with higher proliferation rates, with the latter being associated with poorer outcomes in luminal breast cancers. However, immunotherapy could be an option for patients in with ER+ breast cancer with a high amount of TILs.

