8.0 STATISTICAL ANALYSIS PLAN

8.1 Determination of sample size

Retrospective study (S58910):

Between 2005 and 2010, 285 patients with a ER/PR negative breast cancer larger than 2cm were diagnosed and treated with upfront surgery at the Leuven Multidisciplinary Breast Center (University Hospitals Leuven). Two hundred consecutive patients with available tumor tissue and follow-up data will be included in the proposed retrospective study.

Prospective study (S60100):

The assumptions for the sample size are as follows: More than 600 patients with early breast cancers are diagnosed and treated at the Leuven Multidisciplinary Breast Center (University Hospitals Leuven) on a yearly basis. Twenty percent (120 patients) of these breast cancers are ER/PR negative, half of them Her2 negative and half of them Her2 positive. Of the 120 ER/PR negative patients, 25 percent (30 patients) is expected to receive upfront surgery and 75 percent (90 patients) upfront chemotherapy. After upfront chemotherapy 45 percent of patients is expected to have a residual disease larger than 1cm (40 patients). In total, 70 patients are expected to be eligible for the suggested prospective study. Participation of 50 percent of eligible patients would allow inclusion of 34 patients after 1 year.

Approximately 66 percent (400 patients) of all patients treated at the Leuven Multidisciplinary Breast Center have ER positive breast cancer. 10 percent of these ER+ positive patients is expected to be eligible for this trial taking into account the tumour size after neo-adjuvant therapy and a decent expression of TILs on core biopsy. Participation of 50% of eligible patients would allow inclusion of 20 patients after 1 year. Patients will be included until we have reached the total of 54 patients, independent of the amount of patients in the different cohorts

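### Cohort B is selected on chemotherapy response and cohort A is not, so the unadjusted A-B difference in secondary objective (2) cannot be read as chemotherapy priming; the net direction of bias is unknown.

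*Combined protocol and SAP*

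**What the plan says.** Secondary objective (2) in section 3.2 compares the biomarker change after pembrolizumab in cohort A (upfront surgery, no prior treatment) and cohort B. The hypothesis is directional: "The change in biomarker expression will be higher in cohort B". The objective describes cohort B patients as those who "have received full course of neoadjuvant chemotherapy, and have clear evidence of residual tumor after chemotherapy", and section 5.2.2 makes that an entry rule: "Have residual tumor > 1 cm after neo-adjuvant chemotherapy". Section 2.1 puts the limit at 10 mm or more. No section applies a comparable filter to cohort A.

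The biological argument is in section 4.2.1: "Tumor cells show increased response to immunotherapy after they became more immunogenic by therapy-induced immunogenic cell death".

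The second item numbered (5) in section 3.2 hypothesizes: "Tumors with a high baseline PD-L1 expression and a high amount of TILs are more likely to respond to pembrolizumab". The same sentence extends this, by and/or, to response to neoadjuvant chemotherapy. Section 4.2.3.1 repeats the link between high TILs and response to anti-PD-1/L1 therapy.

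Section 8.1 sizes the filter for ER/PR-negative patients: "After upfront chemotherapy 45 percent of patients is expected to have a residual disease larger than 1cm". It also stops accrual at 54 patients whatever the cohort sizes.

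For the analysis, section 8.2 gives "Differences in evolutions of biomarker expression between cohorts will be estimated using linear models and presented as the mean difference of the change". It names no covariates and does not say what the A-B difference is meant to estimate.

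**The concern.** The rationale invites a causal reading: chemotherapy makes a tumor more immunogenic, so pembrolizumab should move the markers further in B. For that reading, A must stand in for what B would have shown without chemotherapy. It does not, because B has lost the tumors that shrank to 1 cm or less and A has lost nothing comparable. If the same tumors tend to respond to both treatments, B is depleted of likely pembrolizumab reactors. A true priming effect would then look smaller than it is, and a small or null difference could be taken as evidence that chemotherapy does not prime.

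The point is about who reaches cohort B. It is separate from the marker level on the pre-pembrolizumab biopsy and from predicting chemotherapy response.

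**Working it through.** **The plan's own figures (section 8.1).** ER/PR negative: 600 × 0.20 = 120 a year; upfront surgery 120 × 0.25 = 30; upfront chemotherapy 120 × 0.75 = 90; residual disease above 1 cm 90 × 0.45 = 40.5 (stated 40). Eligible 30 + 40 = 70; half is 35 (stated 34). ER positive: 400 × 0.10 × 0.50 = 20. Total 34 + 20 = 54. The figures reproduce to within rounding. Filtered out of B: 90 − 40.5 = 49.5, or 55% of ER/PR-negative chemotherapy patients. No SD, effect size, alpha or power is stated, so everything below rests on assumptions.

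**Two-class illustration.** Assumed: share p = 0.50 of tumors high-TIL at diagnosis, the same in A and in the chemotherapy pool; marker change 1 SD larger in high-TIL tumors; within-class SD 1; true priming effect 0.8 SD; two-sided 5% test. The 54 are split 30:40, giving 54 × 30/70 ≈ 23 in A and 31 in B. The 45% and the 30:40 ratio are stated for ER/PR-negative patients only and are extended here to all 54.

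- High-TIL share in B: q = p × r_high / 0.45, where r_high is the residual rate in high-TIL tumors.
- Residual rate in low-TIL tumors: r_low = (0.45 − p × r_high) / (1 − p).
- Bias of the unadjusted contrast: (q − p) × 1 SD.
- Unadjusted standard error: √[(1 + p(1−p))/23 + (1 + q(1−q))/31], about 0.31 SD.
- Adjusted standard error without selection: √(1/23 + 1/31) = 0.275 SD, slightly larger with imbalance.
- Power from the noncentral t distribution.

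| r_high / r_low | High-TIL share in B (A: 50%) | Bias, SD | Power unadjusted | Power adjusted |
|---|---|---|---|---|
| 45% / 45% (no selection) | 50% | 0 | 72% | 81% |
| 40% / 50% | 44% | −0.06 | 66% | 81% |
| 35% / 55% | 39% | −0.11 | 60% | 81% |
| 30% / 60% | 33% | −0.17 | 53% | 80% |

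Selection itself costs 72 − 66 = 6, 72 − 60 ≈ 13 (from unrounded values) and 72 − 53 ≈ 20 points (from unrounded values). The further 81 − 72 = 9 points is a precision gain that adjustment brings even without selection.

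With p = 0.30 and the same three r_high values, the bias is −0.03, −0.07 and −0.10 SD and unadjusted power is 70%, 67% and 63%.

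**Wider range.** For a high-TIL/PD-L1 share of 20% to 50% and an odds ratio for chemotherapy response of 1.5 to 5, the high share in B falls by 3.5 to 21 percentage points. The contrast shifts by −0.035 to −0.21 times the high-minus-low difference in change. At an odds ratio of 1 the shift is zero.

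**Does the sign hold?** Assume a continuous diagnostic immune score that drives both chemotherapy response (logit slope 0.4 to 1.1 per SD) and the pembrolizumab change (correlation 0.3 to 0.5), with a true B-A difference of 0.50 SD.

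| Cohort A's mean score relative to the chemotherapy pool | Net shift of the unadjusted contrast, SD |
|---|---|
| Equal | −0.06 to −0.24 |
| 0.3 to 0.5 SD lower | −0.10 to +0.15 |
| 0.3 SD higher | −0.15 to −0.39 |

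In every case, adding the diagnostic score to the model returned about 0.50 SD. This works only because the score carries all of the selection in that model.

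**The case against.** **Objective (2) already names residual tumor as part of cohort B.** This stands. As a comparison of the two groups as defined, the contrast is not biased. It is biased only if read as the effect of prior chemotherapy on the pembrolizumab response. Section 4.2.1 encourages that reading, though it claims only that the sequence might be promising.

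**A reader might infer that the contrast is biased against its hypothesis overall.** The documents do not support this. They give no rule for who has surgery or chemotherapy first, the trial is not randomized, and subtype mix is left free. The last table shows that a modest difference between A and the chemotherapy pool can reverse the sign.

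**A reader might infer that B contains no chemotherapy responders.** It does not follow. The rule is absolute residual size, so a large tumor that shrinks markedly but leaves more than 1 cm stays in B.

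**The link between the two responses is a hypothesis.** It is joined by and/or and does not say that the same tumors respond to both. The protocol also expects chemotherapy to raise TILs and lower PD-L1, so diagnostic status may matter less to the pembrolizumab change in B than the illustration assumes.

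**The shift is small beside the noise.** With p = 0.50 it is 0.18 to 0.54 of a standard error. The chance of a reversed estimate rises only from 0.5% to between 0.8% and 1.9%. A reversed result would therefore not be explained by this selection alone.

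**The prevalence is least secure for ER-positive patients.** They are about 20 of the 54, and TILs on core biopsy are an entry condition for A3 and B3.

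**Conclusion.** The concern holds in a limited form. The filter is one-sided and large, at about 55% of ER/PR-negative chemotherapy patients. Under the protocol's own hypothesis this component works against a larger change in B, and section 8.2 neither adjusts for it nor says what the difference estimates. The net direction of bias is not established. The unadjusted A-B difference is a valid description of the two groups but not an estimate of chemotherapy priming, whichever sign it takes.

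The size is illustrative: a bias of about −0.06 to −0.17 SD and 6 to 20 points of power, given 50% high-TIL tumors, a 1 SD larger change in them, a true effect of 0.8 SD and a 23:31 split. Someone comparing 53% with 80% power might charge the whole gap to selection; about 9 points of the gain from adjustment is precision that would appear with no selection at all.

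This is one secondary contrast in a phase 0 study with no power claim. It should be corrected because the remedy is cheap, but it does not affect the primary objective.

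**What to change.** In section 8.2, for secondary objective (2):

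- **Change in Ki67 and CD73:** prespecify a linear model with cohort plus TIL and PD-L1 level on the diagnostic core (pre-chemotherapy in cohort B) as covariates. Report it with the unadjusted estimate.
- **Change in TILs and PD-L1:** report the adjusted estimate only as a sensitivity analysis, because in cohort A the diagnostic core is also the start of the change.
- **Interpretation:** state that the A-B difference applies to tumors leaving more than 1 cm after chemotherapy and is not by itself the effect of chemotherapy on sensitivity to pembrolizumab.

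No new visit or biopsy is needed. Section 7.1.2.6 provides a core biopsy for every patient, inclusion criterion 6 requires an evaluable core for IHC, and secondary objective (1) already depends on pre-chemotherapy readings in cohort B. The cost is SAP wording and two degrees of freedom. Adjustment removes only the selection that diagnostic TILs and PD-L1 capture; other differences in treatment route or subtype remain.
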